- Termination of the study by the Sponsor;
- Patient experiences severe neutropenia/ agranulocytosis (refer to [Section 8.2.4.9](#) for definition and management).

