## 4.6 Treatment Interruptions

Study medication will be interrupted for **ANY** of the following reasons:

- If the patient develops an infection during the study, deferiprone must be interrupted immediately and neutrophil count should be obtained and monitored more frequently (every 2 days if ANC  $<1.5 \times 10^9/L$ ). Patients should be advised to report immediately to their physician any symptoms indicative of infection such as fever, sore throat, and flu-like symptoms. They will be provided with a thermometer, and instructed to seek immediate medical attention at a hospital or clinic if they experience fever (temperature  $>38.0^{\circ}C/100.4^{\circ}F$ ). Body temperature may be measured at the mouth, axilla, or ear. Patients/legal guardians will be provided with an emergency services card with contact information, and will be advised to carry this card at all times. In presence of confirmed fever and/or infection, patients will be required to have their neutrophil counts tested as soon as possible and no later than 24 hours after the symptoms of infection are detected. Therapy with deferiprone can be re-initiated once all symptoms have been resolved and it is deemed safe by the Investigator.
- If temperature is  $>38.0^{\circ}C/100.4^{\circ}F$  and ANC is  $\leq 0.5 \times 10^9/L$ , the following must be done:
  - Commence therapy with antibiotics immediately (treatment should depend on the site of the suspected infection and on local antibiotic policy)
  - Perform a chest x-ray, and collect blood and other relevant cultures (if possible, collect culture samples before initiating antibiotics)
- If the patient develops moderate neutropenia while on deferiprone (refer to [Section 8.2.4.9](#) for definition), therapy must be interrupted immediately and neutrophil count must be obtained and monitored every 2 days. Therapy with deferiprone can be re-initiated once two successive ANCs are  $>1.5 \times 10^9/L$  and it is deemed safe by the Investigator. The patient will be withdrawn from the study if the ANC remains  $<1.5 \times 10^9/L$  by the end of a two-week period (14 days) ([Section 8.2.4.9](#)).

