#### 8.2.4.9 Adverse Event of Special Interest – Neutropenia (Definitions and Management)

##### **Definitions**

*Mild Neutropenia:* A confirmed ANC  $\geq 1.0 \times 10^9/L$  and  $< 1.5 \times 10^9/L$ .

*Moderate Neutropenia:* A confirmed ANC  $\geq 0.5 \times 10^9/L$  and  $< 1.0 \times 10^9/L$ .

*Severe Neutropenia/Agranulocytosis:* A confirmed ANC  $< 0.5 \times 10^9/L$ .

An absolute neutrophil count (ANC) is confirmed as being less than a specified value if two consecutive counts (maximum 3 days apart) are both less than the specified value. If both consecutive counts are below  $1.5 \times 10^9/L$  but not in the same severity category of neutropenia, a third count will be required to determine the severity.

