##### **Management**

*Mild Neutropenia* (two consecutive Absolute Neutrophil Counts  $\geq 1.0 \times 10^9/L$  and  $< 1.5 \times 10^9/L$ ):

Patients receiving deferiprone treatment who experience mild neutropenia (ANC  $\geq 1.0 \times 10^9/L$  and  $< 1.5 \times 10^9/L$ ) should continue treatment. The patient's ANC will be monitored every 2 days until resolution of the event, defined as two consecutive ANC  $\geq 1.5 \times 10^9/L$ . If the ANC remains  $\geq 1.0 \times 10^9/L$  and  $< 1.5 \times 10^9/L$  by the end of a two-week period (14 days):

- The patient will be withdrawn from the study and monitored until resolution of the event.
- The patient will be advised regarding protective isolation.
- The Investigator will notify ApoPharma Inc. by fax.
- The Investigator will examine patient the same day (if possible) including drug history and physical examination.

However, if the patient has a mild neutropenia and develops an infection, therapy must be interrupted immediately and neutrophil count must be obtained and monitored more frequently (every 2 days if ANC  $< 1.5 \times 10^9/L$ ) until resolution of the event, defined as two consecutive ANC  $\geq 1.5 \times 10^9/L$ . Patients should be advised to report immediately to their physician any symptoms indicative of infection such as fever, sore throat, and flu-like symptoms. In presence of confirmed fever and/or infection, they will be required to have their neutrophil counts tested as soon as possible and no later than 24 hours after the symptoms of infection are detected. Patients will be provided with an emergency services card with contact information, and the patient/legal guardian will be advised to carry this card at all times. Therapy with deferiprone can be initiated once all symptoms have been resolved and it is deemed safe by the Investigator.

Moderate Neutropenia (two consecutive Absolute Neutrophil Counts  $\geq 0.5 \times 10^9/L$  and  $< 1.0 \times 10^9/L$ ):

Patients receiving deferiprone treatment who experience moderate neutropenia (ANC  $\geq 0.5 \times 10^9/L$  and  $< 1.0 \times 10^9/L$ ) will immediately interrupt treatment, and the patient's ANC will be monitored every 2 days until resolution of the event, defined as two consecutive ANC  $\geq 1.5 \times 10^9/L$ . If the ANC remains  $< 1.5 \times 10^9/L$  by the end of a two-week period (14 days):

- The patient will be withdrawn from the study and monitored until resolution of the event.

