- Provide protective isolation; if clinically indicated, admit patient to hospital and obtain q4h vital signs.
- The Investigator will notify ApoPharma Inc. by fax.
- The Investigator will examine the patient the same day, if possible, including drug history and physical examination.
- If possible, obtain viral studies (CMV, parvovirus, hepatitis A/B/C), serum ALT, BUN, creatinine, and 10 mL serum split into two 5-mL aliquots for frozen storage, for future analysis.

Severe Neutropenia/Agranulocytosis (two consecutive Absolute Neutrophil Counts  $< 0.5 \times 10^9/L$ ):

Patients receiving deferiprone and who experience severe neutropenia/agranulocytosis (ANC  $< 0.5 \times 10^9/L$ ) will immediately discontinue treatment. The patients will be withdrawn from the study and will be followed daily until two successive ANCs are  $\geq 1.5 \times 10^9/L$ :

- The patient will be withdrawn from the study and monitored until resolution of the event.
- Provide protective isolation; if clinically indicated, admit patient to hospital and obtain q4h vital signs.
- The Investigator will notify ApoPharma Inc. by fax.
- The Investigator will examine the patient the same day, if possible, including drug history and physical examination.
- If possible, obtain viral studies (CMV, parvovirus, hepatitis A/B/C), serum ALT, BUN, creatinine, and 10 mL serum split into two 5-mL aliquots for frozen storage.
- Collect a blood sample to attempt to identify genetic or other biomarkers related to agranulocytosis (optional).
- If possible, obtain bone marrow aspirate for:
  - Histology
  - Progenitor culture
  - Frozen storage (1 mL sample)
- If possible, obtain bone marrow biopsy (minimum length 3 mm).
- Perform septic work-up including chest X-ray, blood, urine and throat cultures.
- Obtain q4h temperatures from patient (monitored by family at home if patient is not in the hospital).
- If warranted, administer granulocyte stimulating factors, such as G-CSF 10 µg/kg, as an inpatient if possible, beginning the same day that the ANC is confirmed as  $< 0.5 \times 10^9/L$ ; administer daily until ANC is  $> 1.5 \times 10^9/L$  on two consecutive days.
- If ANC  $< 0.5 \times 10^9/L$  for 7 days, repeat bone marrow biopsy and aspirate weekly during the period of agranulocytosis, if warranted.

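### After a first ANC below 0.5 in a deferiprone patient without infection or fever, the protocol does not expressly order a hold or a repeat count

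*Protocol*

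**What the plan says.** Protocol 8.2.4.9 defines mild, moderate and severe neutropenia (ANC 1.0 to <1.5, 0.5 to <1.0 and <0.5, all × 10⁹/L) on a confirmed ANC. A count "is confirmed as being less than a specified value if two consecutive counts (maximum 3 days apart") are both under that value. If two counts below 1.5 fall in different categories, "a third count will be required to determine the severity".

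The management rules follow from the grade. Mild cases "should continue treatment" with counts every 2 days. Moderate cases "will immediately interrupt treatment". Severe cases "will immediately discontinue treatment", are withdrawn, and "will be followed daily until two successive ANCs are" at least 1.5. Each block is headed by a requirement for two consecutive counts. Section 4.5 lists "Patient experiences severe neutropenia/ agranulocytosis" among the compulsory reasons for withdrawal and refers to 8.2.4.9 for the definition. Section 4.6 does the same for the moderate hold.

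Infection is handled separately and needs no confirmation. Under 4.6: "If the patient develops an infection during the study, deferiprone must be interrupted immediately". That section also sets out urgent care for fever with an ANC of 0.5 or less.

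**The concern.** Agranulocytosis is the most significant serious event that section 1.2 names for deferiprone, and deaths have been reported after marketing. Section 9.1 warns that it can appear soon after a normal count, so a first count of 0.3 may be its onset. Confirmation before permanent withdrawal is sensible. The difficulty is that the temporary stop waits for the same confirmation.

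The setting makes this matter. Routine counts may be taken at a local laboratory (5.4), and from Week 4 patients receive a month's supply (7.4). A patient without symptoms therefore has drug at home and keeps taking it until the site calls. Section 5.3 requires an ANC above 1.5 before the first dose, yet no written rule stops the next dose after a single count of 0.3 during treatment.

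A pair such as 0.4 then 1.2 raises a second question. The possible grades lead to opposite instructions (continue or stop), and the protocol does not say what to do with the drug until the third count is back.

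**Working it through.** **Step 1: which rules act on a single count.** The plan states no figure to reproduce here, so the check is to set the rules side by side for a deferiprone patient without infection or fever.

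| Protocol section | Trigger | Consequence | Is one low count enough? |
|---|---|---|---|
| 4.5 | Severe neutropenia as defined in 8.2.4.9 | Compulsory withdrawal | No |
| 4.5 | Reaction characterized as life-threatening | Compulsory withdrawal | Only if the investigator so characterizes it |
| 4.5 | Medical reasons, on judgement | Withdrawal allowed | Yes, but optional |
| 4.6 and 8.2.4.9 | Moderate neutropenia | Hold; counts every 2 days | No |
| 8.2.4.9 | Severe neutropenia | Stop and withdraw; any G-CSF dated from the confirmed count | No |
| 5.4 and 8.2.2 | Any haematology result | Review on receipt; prompt interpretation | Yes, but no hold or repeat attached |

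No row orders a hold or a repeat on one count below 0.5.

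**Step 2: doses given in the interval.** Deferiprone is taken three times a day.
- Repeat within the 3-day definition: up to 3 × 3 = 9 doses.
- Routine schedule to Week 26 (weekly, ±3 days, 5.4): nominally 7 days, 7 × 3 = 21 doses. At the window extremes, 7 + 6 = 13 days, 39 doses.
- Routine schedule after Week 26 (every 2 weeks, ±3 days): nominally 14 days, 42 doses. At the extremes, 14 + 6 = 20 days, 60 doses.

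Two counts taken 7 or more days apart would not meet the 3-day definition, so even a second count below 0.5 would not formally be confirmed.

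**Step 3: discordant pairs.** With 0.4 then 1.2, both counts are below 1.5, but the pair fits no management heading. A third count is required, with no stated time and no dosing instruction. Each day of waiting is 3 more doses. A pair such as 0.4 and 0.7 is also unclear: both counts are below 1.0, yet a third is needed to set the grade.

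**Step 4: how many patients.** The incidence is 1.7% (Protocol 1.2, pooled trials). The SAP's sample-size text and section 3.7 give 213 patients finished or withdrawn (142 on deferiprone), 17 ongoing, and a target of 300.
- Planned deferiprone arm: 200 × 0.017 = 3.4 cases. The 142: 142 × 0.017 = 2.4. A text change cannot reach the 142.
- Ongoing, assuming 2:1: 17 × 2/3 = 11.3 patients; 11.3 × 0.017 = 0.19 cases; chance of at least one, 1 − 0.983¹¹ = 17%. If all 17 were on deferiprone, 17 × 0.017 = 0.29 cases.
- Restart to 300: 300 − 213 − 17 = 70; 70 × 2/3 = 46.7 patients; 46.7 × 0.017 = 0.79 cases; chance of at least one, 1 − 0.983⁴⁷ = 55%.

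These are ceilings at the 1.7% rate. Some cases would come with infection or fever, or would already be off drug or under 2-day counts as confirmed moderate or mild neutropenia. The documents do not give the share that remains, or any rate for discordant pairs.

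**The case against.** The case against is substantial, and much of it stands.

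- **A repeat is implied.** Confirmation needs two counts no more than 3 days apart, so a site could fairly infer a repeat within 3 days. The same limit may be read to carry over to a third count that has to pair with the second. A reader might infer that the protocol sets no time limit at all; the text does not support that. What is missing is an express instruction.
- **The interval is not unmanaged.** Section 8.2.2 requires laboratory reports to be interpreted promptly and judged for clinical significance. Section 4.5 allows withdrawal on judgement and requires it for a reaction characterized as life-threatening. A reader might infer that patients with a first count of 0.3 are ignored; the documents do not support this. But these safeguards rest on the investigator's assessment, and a symptomless low count need not be called life-threatening.
- **The body of the severe rule can be read as acting on an ANC below 0.5 alone.** Its heading and the definition both require two counts. Two readings of a stopping rule are a reason to clarify it.
- **Added harm is not shown.** Section 1.2 says agranulocytosis is not dose-related within the therapeutic range and usually resolves once drug is stopped. The documents do not quantify what a few more doses would do, so no claim of expected injury can be made.
- **Other sources.** Section 1.2 refers sites to the prescribing information and Investigator's Brochure for full safety information. They may contain single-count instructions; they were not available.

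**Conclusion.** The point holds in limited form. In a deferiprone patient without infection or fever, the compulsory stop for severe neutropenia waits for confirmation, and no section expressly orders a hold or a repeat after a first ANC below 0.5. The 9 doses are a maximum only if the repeat falls within 3 days; they are not a limit on the whole gap. For two counts below 1.5 in different categories there is no interim dosing rule and no express deadline for the third count.

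The practical size is small at this stage: about 11 patients and at most 0.2 expected cases, rising by at most 0.8 if enrolment restarts and reaches 300. These figures assume 2:1 allocation among ongoing and future patients. They also assume that the 1.7% rate carries over from trials in which, by section 1.4, most patients had thalassemia. For ongoing patients past the 5-month peak described in 1.2, the rate is probably too high. The 3.4 and 2.4 whole-arm figures should not be read as patients who would be dosed through agranulocytosis, since an unknown share is caught by the existing rules. Confidence is medium. The case for change is that it is cheap and removes an ambiguity about the drug's most serious named risk.

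**What to change.** Add to Protocol 8.2.4.9, with a cross-reference in 4.6:

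> Any single ANC <0.5 × 10⁹/L in a patient on deferiprone: hold deferiprone on receipt of the result and repeat the ANC within 24 hours. If two consecutive counts below 1.5 × 10⁹/L fall in different categories and either is below 1.0 × 10⁹/L, hold deferiprone and obtain the third count within 24 hours. Confirmation is used only to assign severity and decide withdrawal. After such a hold, restart only after two consecutive ANCs >1.5 × 10⁹/L and when the Investigator deems it safe.

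The 24-hour limit is the one 4.6 already uses for counts on signs of infection. The restart standard is the one 4.6 sets after moderate neutropenia; a lower threshold would weaken that safeguard.

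**Cost in doses.** A year of treatment is 52 × 7 × 3 = 1,092 doses. For a transient low count with daily counts, the hold costs about 6 doses with same-day results (0.55%) or 9 with next-day results (0.82%). It costs 3 if both normal counts fit in the first 24 hours (0.27%). Patients who recover only to 1.0 to <1.5 stay off drug longer, where the mild rule alone would have let them continue.

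**Cost in process.** This is a safety amendment. Section 14.6 requires ethics approval and regulatory notification or approval before use, across eight countries (SAP 3.4). It also allows immediate action against an apparent immediate hazard; whether this qualifies is for the sponsor to judge. The 17 ongoing patients are due to finish by October 2019, so approval may come too late for some. SAP 3.7 leaves any restart to a decision based on the DSMB's advice, and the text should be in place before then.

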##### **Management**

*Mild Neutropenia* (two consecutive Absolute Neutrophil Counts  $\geq 1.0 \times 10^9/L$  and  $< 1.5 \times 10^9/L$ ):

Patients receiving deferiprone treatment who experience mild neutropenia (ANC  $\geq 1.0 \times 10^9/L$  and  $< 1.5 \times 10^9/L$ ) should continue treatment. The patient's ANC will be monitored every 2 days until resolution of the event, defined as two consecutive ANC  $\geq 1.5 \times 10^9/L$ . If the ANC remains  $\geq 1.0 \times 10^9/L$  and  $< 1.5 \times 10^9/L$  by the end of a two-week period (14 days):

- The patient will be withdrawn from the study and monitored until resolution of the event.
- The patient will be advised regarding protective isolation.
- The Investigator will notify ApoPharma Inc. by fax.
- The Investigator will examine patient the same day (if possible) including drug history and physical examination.

However, if the patient has a mild neutropenia and develops an infection, therapy must be interrupted immediately and neutrophil count must be obtained and monitored more frequently (every 2 days if ANC  $< 1.5 \times 10^9/L$ ) until resolution of the event, defined as two consecutive ANC  $\geq 1.5 \times 10^9/L$ . Patients should be advised to report immediately to their physician any symptoms indicative of infection such as fever, sore throat, and flu-like symptoms. In presence of confirmed fever and/or infection, they will be required to have their neutrophil counts tested as soon as possible and no later than 24 hours after the symptoms of infection are detected. Patients will be provided with an emergency services card with contact information, and the patient/legal guardian will be advised to carry this card at all times. Therapy with deferiprone can be initiated once all symptoms have been resolved and it is deemed safe by the Investigator.

Moderate Neutropenia (two consecutive Absolute Neutrophil Counts  $\geq 0.5 \times 10^9/L$  and  $< 1.0 \times 10^9/L$ ):

Patients receiving deferiprone treatment who experience moderate neutropenia (ANC  $\geq 0.5 \times 10^9/L$  and  $< 1.0 \times 10^9/L$ ) will immediately interrupt treatment, and the patient's ANC will be monitored every 2 days until resolution of the event, defined as two consecutive ANC  $\geq 1.5 \times 10^9/L$ . If the ANC remains  $< 1.5 \times 10^9/L$  by the end of a two-week period (14 days):

- The patient will be withdrawn from the study and monitored until resolution of the event.
- Provide protective isolation; if clinically indicated, admit patient to hospital and obtain q4h vital signs.
- The Investigator will notify ApoPharma Inc. by fax.
- The Investigator will examine the patient the same day, if possible, including drug history and physical examination.
- If possible, obtain viral studies (CMV, parvovirus, hepatitis A/B/C), serum ALT, BUN, creatinine, and 10 mL serum split into two 5-mL aliquots for frozen storage, for future analysis.

Severe Neutropenia/Agranulocytosis (two consecutive Absolute Neutrophil Counts  $< 0.5 \times 10^9/L$ ):

Patients receiving deferiprone and who experience severe neutropenia/agranulocytosis (ANC  $< 0.5 \times 10^9/L$ ) will immediately discontinue treatment. The patients will be withdrawn from the study and will be followed daily until two successive ANCs are  $\geq 1.5 \times 10^9/L$ :

- The patient will be withdrawn from the study and monitored until resolution of the event.
- Provide protective isolation; if clinically indicated, admit patient to hospital and obtain q4h vital signs.
- The Investigator will notify ApoPharma Inc. by fax.
- The Investigator will examine the patient the same day, if possible, including drug history and physical examination.
- If possible, obtain viral studies (CMV, parvovirus, hepatitis A/B/C), serum ALT, BUN, creatinine, and 10 mL serum split into two 5-mL aliquots for frozen storage.
- Collect a blood sample to attempt to identify genetic or other biomarkers related to agranulocytosis (optional).
- If possible, obtain bone marrow aspirate for:
  - Histology
  - Progenitor culture
  - Frozen storage (1 mL sample)
- If possible, obtain bone marrow biopsy (minimum length 3 mm).
- Perform septic work-up including chest X-ray, blood, urine and throat cultures.
- Obtain q4h temperatures from patient (monitored by family at home if patient is not in the hospital).
- If warranted, administer granulocyte stimulating factors, such as G-CSF 10 µg/kg, as an inpatient if possible, beginning the same day that the ANC is confirmed as  $< 0.5 \times 10^9/L$ ; administer daily until ANC is  $> 1.5 \times 10^9/L$  on two consecutive days.
- If ANC  $< 0.5 \times 10^9/L$  for 7 days, repeat bone marrow biopsy and aspirate weekly during the period of agranulocytosis, if warranted.

## 9 PROCEDURES IN CASE OF MEDICAL EMERGENCY

The Investigator is responsible for ensuring that procedures and expertise are available to cope with medical emergencies during the study period. An emergency may constitute an SAE.

### 9.1 Precautions/Overdose

An overdose is defined as taking more than the prescribed individual dose or more than maximum daily dose.

Deferiprone:

Deferiprone use can be associated with neutropenia, including agranulocytosis, the cause of which is currently unknown. Because of the awareness of this risk, weekly monitoring for neutrophil count was proposed in the first marketing authorization application for deferiprone and has been in effect since. However, a recent review of both clinical and post-marketing data accumulated over the last two decades confirmed that deferiprone-induced agranulocytosis is not dose-related within the therapeutic range, and its occurrence peaks at 5 months after initiation of therapy, declining in frequency after this period. It was concluded that weekly monitoring is a prudent approach but that it does not preclude agranulocytosis from occurring and it could even provide false security, as agranulocytosis could occur shortly after the finding of a normal neutrophil count. The relevance of weekly monitoring of the neutrophil count appears to decrease even further after the first six months of therapy, when agranulocytosis occurs less often. Based upon analysis of data collected over the past 20 years, it appears that patient education may be the key to minimizing risks associated with agranulocytosis during deferiprone therapy. A better approach to minimizing the risks in patients receiving long-term deferiprone therapy is for ANC monitoring to be done weekly only at the beginning of the treatment and to emphasize the importance of educating patients on the need to immediately stop deferiprone and to maintain ANC monitoring upon signs of infection.

Neurological disorders such as cerebellar symptoms, diplopia, lateral nystagmus, psychomotor slowdown, hand movements, and axial hypotonia have been observed in children who were treated with deferiprone at doses more than twice the maximum recommended dose of 100 mg/kg/day for transfusion-related iron overload for up to 16 months. The neurological disorders progressively regressed after deferiprone discontinuation.

Deferoxamine:

Inadvertent administration of an overdose or inadvertent intravenous bolus administration/rapid intravenous infusion may be associated with hypotension, tachycardia, and gastrointestinal disturbances; acute but transient loss of vision, aphasia, agitation, headache, nausea, pallor, CNS depression including coma, bradycardia and acute renal failure have been reported. Acute respiratory distress syndrome has been reported following treatment with excessively high intravenous doses of deferoxamine in patients with acute iron intoxication and in patients with thalassemia.

Overdose per se will not be reported as an AE. The signs and symptoms or clinical sequelae resulting from overdose will be reported if they fulfill the AE or SAE definition.

